### RANDOMIZATION PHASE:

Subjects scheduled to undergo open subpectoral biceps tenodesis will be randomized to either Pecs II block with bupivacaine 0.25% or subpectoral surgical skin infiltration with bupivacaine 0.25%. A randomization scheme will be created prior to start of study enrollment using the randomizer.org website to generate the assignment. Block randomization is commonly used in clinical trial design to reduce bias and achieve balance in the allocation of participants to treatment arms throughout the course of the study. Randomized block design allows us to account for variables so that observed differences are largely due to true differences between treatments and not to the variable. The greatest variable affecting the PECS study is surgical technique and it could possibly vary throughout the duration of the study. We will create blocks of four patients and in each block, two patients will be assigned to the PECS II group, and two to the infiltration group. Thus, patients in both groups will be evenly spread from the beginning to the end of the study period.

A research coordinator will place the randomization results in sealed opaque envelopes prior to recruitment. Each subject enrolled in the study will be assigned a number and the sealed envelope assigning the subject to the PECS II versus surgical infiltration arm will be opened on the day of surgery after the patient has signed consent agreeing to participate in the study.

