### TREATMENT PHASE:

Patients in both groups will receive an interscalene nerve block with 20 mL 0.5% bupivacaine. Subjects in the Pecs II block group will receive 20mL 0.25% bupivacaine; 20ml will be injected between pectoralis minor and serratus anterior muscles. The subpectoral surgical skin infiltration group will receive 15mL bupivacaine 0.25% by the surgeon. These medications will be obtained from the operating room omniceil. Neither the anesthesiologist nor surgeon will be blinded to the patient's group assignment, as they are the ones administering the treatment. All other stakeholders (patient, other caregivers, and research staff collecting the data) will be blinded to the patient's group assignment.

[figure not shown]

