### **3 Study Enrollment and Withdrawal**

The researchers will approach patients scheduled for shoulder arthroscopy with open biceps tenodesis who are eligible for participation in the study. Anesthesiology attendings, fellows, residents, and authorized researchers will consent and enroll patients pre-operatively.

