#### **3.2 Exclusion Criteria**

1. Patients younger than 18 and older than 75;
2. Patients with a history of chronic pain that have used opioids for pain management for 3 months or longer;
3. Patients who are allergic to oxycodone;
4. Patients with diagnosed or self-reported cognitive dysfunction;
5. Patients with a history of neurologic disorder that can interfere with pain sensation;
6. Patients with a history of drug or recorded alcohol abuse;
7. Patients who are unable to understand or follow instructions;
8. Patients with severe liver disease, renal insufficiency, congestive heart failure, and/or significant heart disease;
9. Patients with an allergy or contraindication to any of the medications used in the study, or patients with a contraindication to any study procedures;
10. Patients with a BMI over 45;
11. Any patient that the investigators feel cannot comply with all study related procedures;
12. NYU Langone Health students, residents, faculty or staff members.

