##### **Process of Consent**

The consent for participation will be obtained on day of surgery in pre-operative holding room by the regional anesthesiology fellows, Attending Physicians, or authorized researchers that are members of the study team. Extensive discussion of risks and possible benefits of participation will be provided to the participants and their families. Consent forms will be IRB-approved, and participants will be asked to read and review the document. The investigator will explain the research study to the participant and answer any questions that may arise. All participants will receive a verbal explanation suited to their comprehension of the purposes, procedures and potential risks as well as their rights as research participants. Participants will have the opportunity to carefully review the written consent form and ask questions prior to signing. The participants will have the opportunity to discuss the study with their surrogates or think about it prior to agreeing to participate. The participant will sign the informed consent document prior to any procedures being done specifically for the study. The participants may withdraw consent at any time throughout the course of the trial. A copy of the signed informed consent document will be given to the participants for their records. The rights and welfare of the participants will be protected by emphasizing that the quality of their medical care will not be adversely affected if they decline to participate in this study. If you are unable to obtain consent at an earlier time, subjects will be given a copy of the informed consent form at their pre-surgical visit to allow them time to read through it, discuss with their relatives, and contact the study team with any questions prior to their surgery.

CONFIDENTIAL

This material is the property of the NYU School of Medicine and Langone Medical Center. Do not disclose or use except as authorized in writing by the study sponsor

A copy of the signed informed consent document will be given to the patient, placed in the patient's electronic medical record and the original copy will be stored in the research regulatory binder. Any alteration to the standard consent process (e.g., use of a translator, consent document presented orally, etc.) and the justification for such alteration will likewise be documented.

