### **4.2 Study Schedule**

#### **4.2.1 Screening**

##### **Screening Visit (Pre-surgical office visit -30 to -1 days)**

- Review medical history to determine eligibility based on inclusion/exclusion criteria.
- Review medications history to determine eligibility based on inclusion/exclusion criteria.
- Perform medical examinations needed to determine eligibility based on inclusion/exclusion criteria.
- Schedule study visits for participants who are eligible and available for the duration of the study.
- Provide participants with further details regarding their participation on day of surgery and follow up.

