#### **4.2.2 Enrollment/Baseline**

##### **Enrollment/Day of surgery (Visit 1, Day 0)**

- Obtain informed consent of potential participant verified by signature on study informed consent form.
- Verify inclusion/exclusion criteria.
- Complete baseline global health and pain assessment
- Randomize to Pecs II or surgical infiltration treatment group
- Perform surgery with analgesic intervention determined by randomization
- Record vital signs, opioid usage, results of examinations, other pain assessments.
- Continue observation in PACU preceding discharge, including administration of VAS scores, pain questionnaire, and opioid usage monitoring.

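### A printed fixed block of four, with no rule keeping staff who know earlier allocations from enrolling later patients, leaves some allocations open to inference; the likely effect is small and the safeguards are cheap.

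*Combined protocol and SAP*

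**What the plan says.** - **Block structure.** Section 2.1 (Randomization Phase) states: "We will create blocks of four patients and in each block, two patients will be assigned to the PECS II group". The other two go to infiltration. The stated reason is that surgical technique may change during the study, so the arms should stay evenly spread over time.
- **Who knows the allocation.** Section 2.1 (Treatment Phase): "Neither the anesthesiologist nor surgeon will be blinded". Patients and other caregivers are blinded, and the text adds: "research staff collecting the data) will be blinded".
- **Who enrols.** Section 3: "Anesthesiology attendings, fellows, residents, and authorized researchers will consent and enroll patients pre-operatively". Section 3.4 has consent taken "by the regional anesthesiology fellows, Attending Physicians, or authorized researchers that are members of the study team".
- **Room for discretion.** Section 3.2, criterion 11, excludes "Any patient that the investigators feel cannot comply with all study related procedures". Section 4.2.2 lists "Verify inclusion/exclusion criteria" on the day of surgery, after consent and before randomization.
- **Safeguards.** First screening is at the "Pre-surgical office visit -30 to -1 days" (Section 4.2.1). Envelopes are sealed and opaque and are opened after signed consent (Section 2.1). An authorized researcher hands them to the anesthesiologist after consent (Section 6.4).
- **List preparation.** Section 2.1 names randomizer.org and a research coordinator. Section 6.4 names randomization.com and a person who is not a stakeholder.
- **Primary test.** Sections 6.1 and 6.2 plan an unadjusted t-test, or a rank test if the data are not normal. PROMIS Pain Intensity is collected at baseline (Sections 2.1 and 4.2.2; attachment 16.2) but is not used in that test.

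**The concern.** In a 2:2 block of four, anyone who knows the block boundaries and the earlier allocations can sometimes deduce the next one without touching an envelope. Anesthesiology staff may enrol, and the treating anesthesiologist learns each allocation. The documents place no barrier between those two roles. A person with a guess about the next assignment can decide whom to approach, or how to apply a judgement-based criterion on the day of surgery. If those decisions track expected opioid use, the arms differ at baseline for a reason that no analysis can reliably undo.

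The unused baseline pain score raises a different and lesser question, about precision rather than bias.

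**Working it through.** **The plan's own figure.** Section 6.3 gives means of 25 and 32 mg (difference 7), SD 13, two-sided alpha 0.05, power 0.90 and 72 per group. The normal approximation is 2 × [13 × (1.960 + 1.282) / 7]² = 72.5, or 73 per group; the t-test needs 74. The stated 72 reproduces within two patients. t-test power is 0.894 at 72 per group and 0.923 at the 80 to be enrolled.

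**Allocations certain in advance.** There are 6 equally likely orders of a 2:2 block. Assume that the enroller knows the block boundaries and knows each earlier allocation in the block with probability p.
- Positions 1 and 2 are never certain.
- Position 3 is certain if the first two are equal (probability 1/3) and both are known (p²): p²/3.
- Position 4 is certain if both earlier members of the completed arm are known: p².
- Share of all allocations: (p²/3 + p²)/4 = p²/3.

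| p | Certain in advance | Of 160 | Best guess correct |
|---|---|---|---|
| 1 | 33.3% | 53 | 70.8% |
| 0.75 | 18.8% | 30 | 64.6% |
| 0.5 | 8.3% | 13 | 59.9% |
| 0.25 | 2.1% | 3 | 55.4% |

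The best-guess column comes from enumerating the same 6 orders; chance is 50%. At p = 1 it is (1/2 + 2/3 + 2/3 + 1)/4 = 0.708.

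**Effect of varying the block size.** With sizes 4, 6 and 8 mixed at random on one list, and p = 1, simulation gives a best-guess rate of about 68% against 71%. The certain share falls to about 2%, but most of the guessing advantage remains. Lowering p from 1 to 0.5 with fixed fours brings the best-guess rate down to 60%. What enrollers know therefore matters more than block size.

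**Baseline adjustment.** The documents give no correlation r between baseline pain and 24-hour opioid use, so r is assumed. With residual SD 13 × √(1 − r²) and 80 per arm, formula power is:
- r = 0: 0.923
- r = 0.1: 0.925
- r = 0.2: 0.932
- r = 0.3: 0.944
- r = 0.4: 0.958

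The next table is a simulation with 20,000 runs per cell, robust (HC3) standard errors and a baseline score rounded to 3–15. The skewed case assumes gamma data with SD 13.

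| r | Normal: adjusted / t-test | Skewed: adjusted / t-test / Wilcoxon |
|---|---|---|
| 0.1 | 0.922 / 0.923 | 0.918 / 0.921 / 0.955 |
| 0.2 | 0.928 / 0.922 | 0.928 / 0.923 / 0.957 |
| 0.3 | 0.939 / 0.922 | 0.934 / 0.918 / 0.953 |
| 0.4 | 0.956 / 0.924 | 0.951 / 0.921 / 0.955 |

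The simulation error of one cell is about √(0.92 × 0.08 / 20,000) = 0.002, so nothing is gained at r = 0.1. Under the assumed skew, the adjusted test trails the Wilcoxon test by 3.7, 2.9, 1.9 and 0.4 percentage points in turn.

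**The case against.** The strongest reply is that the safeguards already limit the problem. Patients are screened in the office one to thirty days ahead, envelopes stay sealed until consent is signed, several people enrol, and there are two sites. Criterion 11 concerns ability to comply, not expected opioid use. Small blocks were also chosen for a reason, since they keep the arms level if surgical technique drifts. All of this stands, and it is why the point is minor. It does not close the gap, because sealing an envelope does not prevent inference from earlier allocations.

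A reader might infer several stronger things that the documents do not support:
- **That concealment was breached, or that one person treats and then enrols.** The text permits the overlap but reports no instance of it.
- **That type I error is badly inflated.** Any such figure needs an assumed shift d, up for patients guessed to one arm and down for the other. A d of 3 mg is then a 6 mg gap, nearly the whole 7 mg planned difference. The documents give no basis for that size.
- **That one list serves both sites.** Section 6.4 speaks of assignments for all 160 participants but does not say whether the list is shared or kept per site. How much the second site hides is therefore unknown.
- **That the envelope preparer is not independent.** The two descriptions may fit one person; the text does not say.
- **That the unadjusted t-test is an error.** It is valid and has power 0.923 under the plan's own inputs.

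**Conclusion.** The point holds as a potential weakness in allocation concealment, worth considering. The fixed block, the unblinded treating staff and the permitted enrolment by anesthesiology staff are all in the text, and no rule separates knowledge of earlier allocations from later enrolment. Full knowledge of the running block sets the ceiling of one allocation in three. With partial knowledge the exposure falls with the square of p, and the likely effect on the result is small. The value of p is an assumption throughout.

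The mismatch between Sections 2.1 and 6.4 on the generator and on the description of the preparer is a plain textual inconsistency, whatever p is.

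Baseline adjustment is a separate, optional gain in precision. It ranges from nothing at r = 0.1 to about 3.5 percentage points of formula power at r = 0.4 (0.958 − 0.923). It is no substitute for the planned rank test if the data are skewed.

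**What to change.** 1. Have day-of-surgery consent and the final eligibility check in Section 4.2.2 done by authorized researchers who are not told earlier allocations. Sections 3 and 3.4 already let authorized researchers take consent.
2. For any allocation numbers not yet used, vary the block sizes at random, starting after the running block ends. Keep the sizes small, so that the arms stay evenly spread over time as Section 2.1 intends, and keep them out of documents that enrollers see. The documents do not give enrolment status, so this may apply to only part of the list. On its own it helps little.
3. Reconcile Sections 2.1 and 6.4 on the generator and on who prepares the envelopes. State that the preparer does not consent or enrol, and whether the list is shared across sites.
4. Optional: prespecify a mean difference in 24-hour oxycodone-equivalents adjusted for baseline PROMIS Pain Intensity, with robust standard errors. Keep the rank test in the plan for non-normal data. If power is cited in support, show the full range of r, including 0.1.

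The cost is a protocol amendment with IRB approval (Section 10.2), some consent staffing and one new list for unused numbers. No extra patients or data fields are needed. A 4/6/8 list cut at 160 ends with an arm imbalance of 0.6 on average and 4 at most; power at 78/82 is 0.9227 against 0.9229 at 80/80. Balance over time is looser: the imbalance inside a block of eight can reach 4, against 2 in a block of four. That is the reason to keep the sizes small.

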## **1 Background and Specific Aims**

Biceps tendinopathy can range from inflammatory to degenerative pathology and can often contribute to anterior shoulder pain. This pain is generally located at the anteromedial aspect of the shoulder in the area of the intertubercular groove. Surgical treatment by biceps tenodesis can help increase strength and decrease pain in patients that have failed non-operative management. Although there are many variations to the surgical approach, one approach that has been shown effective is the open subpectoral biceps tenodesis.

For arthroscopic and open shoulder surgeries, assuming there are no contra-indications, anesthesiologists at our institution most often perform interscalene brachial plexus blocks along with IV sedation. The brachial plexus provides innervation to most of the shoulder joint and adjacent soft tissue. Nerves that require blockade to achieve effective analgesia include the subscapular, axillary, lateral pectoral, and suprascapular nerves. These nerves are anesthetized with the interscalene brachial plexus block which targets the C5-6 nerve roots and spares the inferior trunk of the brachial plexus. When an open subpectoral biceps tenodesis is being performed, either alone or with shoulder arthroscopy, a vertical incision is made along the anteromedial aspect of the arm centered over the pectoralis major tendon. Unfortunately, this area of the upper arm is not anesthetized by the interscalene brachial plexus block.

The anteromedial aspect of the upper arm is typically innervated by the medial brachial cutaneous nerve and the medial pectoral nerve, which arise from the inferior trunk of the brachial plexus, along with the intercostobrachial nerve, which originates from the T2 nerve root. In order to anesthetize this area, one can consider utilizing the Pecs II block. The Pectoralis nerve blocks (Pecs) were initially intended for breast surgeries; however, they have also become a popular substitute for paravertebral blocks and thoracic epidurals following thoracic and abdominal wall surgeries. The Pecs I block consists of an injection of local anesthesia between the pectoralis major and minor

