## 6.4 Enrollment/Randomization/Masking Procedures

We will utilize randomization.com to generate a block randomization assignments for all 160 participants. Someone that is not a stakeholder in the study will make randomization envelopes, which include the study ID number, the treatment assignment, and dosage specifics. These randomization envelopes will then be distributed to the anesthesiologist pre-operatively by the authorized researcher after informed consent is obtained.

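### The protocol does not keep the allocation sealed until the interscalene block common to both arms is done, so the unblinded anesthesiologist may know the arm while giving it

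*Combined protocol and SAP*

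**What the plan says.** Section 2.1 (Randomization phase) says that the sealed envelope "will be opened on the day of surgery after the patient has signed consent agreeing to participate in the study". Signed consent is the only trigger given.

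Section 6.4 says that the envelopes hold "the study ID number, the treatment assignment, and dosage specifics" and are "distributed to the anesthesiologist pre-operatively by the authorized researcher after informed consent is obtained".

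Section 2.1 (Treatment phase) opens with the co-intervention: "Patients in both groups will receive an interscalene nerve block with 20 mL 0.5% bupivacaine". It adds that "Neither the anesthesiologist nor surgeon will be blinded", because these clinicians administer the treatment. No exception is made for the block that the arms share.

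Section 4.2.2 lists "Randomize to Pecs II or surgical infiltration treatment group" after consent and baseline assessment and before surgery with the allocated analgesic. It does not list the interscalene block at all.

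Section 1 indicates who normally gives the shared block: "anesthesiologists at our institution most often perform interscalene brachial plexus blocks along with IV sedation".

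The volume of the shared block is 20 mL in the Protocol Summary, the arm table in Section 2 and Section 2.1, but 15 mL in Section 4.1.1.

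**The concern.** The interscalene block is meant to be identical in both arms, so the allocation serves no purpose until it is finished. The stated reason for unblinding covers the Pecs II block and the infiltration. It does not cover a block that everyone receives.

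Section 1 describes the interscalene block as the source of analgesia for most of the shoulder joint. The primary endpoint in Section 6.2 counts opioids during surgery and through 24 hours, so the quality of this block bears directly on it. If the operator knows the arm, then the care taken, a repeat attempt or the volume injected could differ by arm. Any such difference would be counted as a treatment effect. Blinding the patient does not prevent this, and analysis by intention to treat does not remove it.

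Two features make it harder to rule out afterwards. The volume conflict means that either volume could be given and still match some section of the protocol. The data items listed in Section 6.2.1 also do not include the interscalene volume, the number of attempts or whether the block succeeded.

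**Working it through.** **Step 1. What fixes the order of events?**

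| Place | What it fixes | What it leaves open |
|---|---|---|
| 2.1, Randomization phase | Day of surgery, after consent | Before or after the interscalene block |
| 6.4 | Hand-over to the anesthesiologist before surgery | When the envelope is opened |
| 4.2.2 | Randomization before surgery | The interscalene block is not listed |
| 2.1, phase order | Treatment described after randomization | Whether the headings are a strict sequence |

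No row requires the shared block to come first, and none assigns it to an operator unaware of the arm. Equally, no row states that opening comes first. The text permits both orders, and the phase order points towards earlier opening.

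**Step 2. The plan's own sample size (Section 6.3).** Inputs: difference 32 − 25 = 7 mg, SD 13 mg, two-sided α 0.05, power 0.90.

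n per arm = 2 × (1.960 + 1.282)² × 13² / 7² = 2 × 10.51 × 169 / 49 = 72.5, rounded up to 73. The plan states 72, so its figure is reproduced to within one patient. Power for the t test is 0.894 at 72 per arm and 0.923 at 80 per arm.

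**Step 3. Standard error at 80 per arm.** SE = 13 × √(2/80) = 2.06 mg.

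**Step 4. Illustrative shift.** The documents give no rate of inadequate interscalene blocks and no opioid cost of one. I assume that the rate differs between arms by 2 to 10 percentage points because the operator knows the arm, and that an inadequate block adds 10 to 20 mg. Shift = rate difference × added opioid.

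- 0.02 × 10 = 0.2 mg, which is 0.2/7 = 3% of the planned effect
- 0.05 × 20 = 1.0 mg, or 14%
- 0.10 × 20 = 2.0 mg, or 29%

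**Step 5. Rejection rate with no true effect.** By the normal approximation, with b the shift, P = Φ(−1.96 + b/SE) + Φ(−1.96 − b/SE).

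- b = 0.2 mg: 0.051
- b = 1.0 mg: 0.078 (t test 0.077)
- b = 2.0 mg: 0.16 (t test 0.162)

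**Step 6. Shift against Pecs II.** If the true difference is 7 mg and the shift runs the other way, the observed difference centres on 6 mg or 5 mg. Power at 80 per arm then falls from 0.923 to 0.827 (1 mg shift) or 0.676 (2 mg shift).

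**The case against.** A reader might infer that the protocol has the envelope opened before the interscalene block. The documents do not support that as a fact. Section 2.1 fixes only the day and the consent, and a block given before theatre is itself pre-operative, so the hand-over in 6.4 does not settle the order. The schematic in Section 2.2 and a figure in Section 2.1 are not in the text available here and might show the sequence. This part of the objection stands.

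The mechanism also has no stated direction. Both arms have the same nominal block, so a difference would need unequal effort, different technique or a departure from the specified volume. The figures in Step 4 are assumptions, and the low end (0.051) cannot be told apart from 0.05. This stands too, and it limits the weight of the point.

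A reader might further infer that early allocation wastes randomized places on cancelled cases or failed blocks. No such rate is given, the plan enrols 80 per arm against 72 needed, and losses before the arms diverge would be expected to be similar. I do not press this.

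Finally, the remedy leaves a more direct route open. The same unblinded anesthesiologist is present during surgery, and intraoperative opioids count in the primary endpoint. That is true, but it is no reason to leave open a route that can be closed at almost no cost.

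**Conclusion.** The point holds as a cheap improvement. The protocol does not conceal the arm until the shared block is complete, and knowledge of the arm is not needed for that block. What is established is a gap in the procedure. That the arm is in fact known at that moment, and that delivery would then differ, are possibilities the text leaves open.

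Neither the size nor the direction of any bias can be derived from the documents. An assumed shift of 1 to 2 mg would move the null rejection rate from 0.05 to about 0.08 to 0.16, or cost power if it ran against Pecs II. A shift of 0.2 mg would not matter. These figures rest on the plan's SD of 13 mg, 80 analysed per arm, and a shift that is consistent across patients. The sample size does not change.

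**What to change.** In Sections 2.1, 4.2.2 and 6.4:

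- State that the envelope stays sealed until the interscalene block is complete. Add the block to the day-of-surgery list in 4.2.2, before randomization.
- State that the treating anesthesiologist then opens it, out of view of the patient and of research staff who collect outcome data. The researcher who hands it over should not see the contents, since Section 2.1 requires data collectors to be blinded and also has an authorized research member score pain in the PACU.
- Record the interscalene volume given, the time the block was completed and the time the envelope was opened.

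Reconcile the interscalene volume across the Protocol Summary and Sections 2, 2.1 and 4.1.1, so that the shared block is specified once and is the same in both arms.

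Acknowledge as a limitation that an unblinded anesthesiologist may still influence intraoperative opioid use.

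The cost is protocol wording, three extra data items and a few minutes at the bedside to prepare the second injection while keeping the patient unaware of the arm. No extra patients are needed.
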